# **Objectives and Endpoints:**

Objectives	Endpoints
Primary	
• Explore the safety of IFX-1 for the treatment of subjects with pyoderma gangrenosum	• Occurrence, nature and intensity of treatment emergent adverse events (TEAEs), related TEAEs, serious TEAEs, and adverse events of special interest
Key Secondary	
• Explore the efficacy of IFX-1 for the treatment of pyoderma gangrenosum	
 
Responder rate defined as Physician's Global Assessment ≤3 of target ulcer at Visits V4, V6, V10, and V16 (End of Treatment [EOT])
 
Time to complete closure of pyoderma
 

	gangrenosum target ulcer (investigator assessment)
• Explore additional clinical outcome parameters in subjects with pyoderma gangrenosum under the treatment with IFX-1	• Percentage change in wound area and wound volume (wound healing) of target ulcer between Visits V1-V4, V1-V6, V6-V10; V10-V16, and V1-V16 (photographic assessment)
	• Rate of change per day in area of target ulcer (photographic assessment)
	• Number of subjects with a decrease in area of target ulcer of 50% or more at Visit V16 (EOT) compared to baseline (photographic assessment)
	• Number of subjects with a decrease in area of target ulcer of 100% at Visit V16 (EOT) compared to baseline (remission) (photographic assessment)
	• Degree of erythema and border elevation of the target ulcer compared to baseline at Visits V4, V6, V10, and V16 (EOT) (investigator assessment)
	• Mean change from baseline in pain assessed by Numeric Rating Scale (NRS) at Visits V4, V6, V10, and V16 (EOT)
	• Mean change from baseline in Dermatology Life Quality Index (DLQI) at Visits V4, V6, V10, and V16 (EOT)

InflaRx	Clinical Study Protocol,
	Version 4.0 Including Amendment 02, 14 May 2020
IFX-1	IFX-1-P2.7

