There is substantial medical need for effective treatment for pyoderma gangrenosum. Subjects have severe pain, long times to complete healing, and frequent relapses. The risk of death is 3-times higher than controls (Langan 2012), with an inpatient death rate of 10-20% (Adisen 2016, Cabalag 2015, Ye 2014). However, as subjects with pyoderma gangrenosum usually have notable comorbidities, death may be due to these, an underlying associated disorder, or treatment. Response rates in subjects suitable for topical treatment has been reported to be only about 50%, but the response rates with biologicals has been reported to be between 20% and 90%.

There is no "gold standard" for therapy (Gameiro 2015) or product license for use. Treatment comprises wound dressings, and medicinal treatments (e.g., corticosteroids, tacrolimus, sodium cromoglicate, nicotine, 5-aminosalicylic acid, cyclosporine, activated protein C, timolol gel) (Gameiro 2015, Reichrath 2005, Cabalag 2015, Cozzani 2014, Kim 2014, Moreira 2017). The treatment for more aggressive disease includes steroids, cyclosporine, azathioprine, sulfasalazine, dapsone, thalidomide, minocycline, clofazimine, methotrexate, mycophenolate mofetil, tacrolimus, intravenous immunoglobulin, cyclophosphamide, systemic antibiotics with anti-inflammatory activity (tetracyclines, vancomycin, rifampicin, and mezlocillin), and biologicals such as anakinra (anti-II1 Receptor), especially with PAPA syndrome, anti-TNF alpha, especially with inflammatory bowel disease (etanercept reported not be effective), and ustekinumab (anti IL12, IL-23).

The assessment of the response to therapy is hampered by the small number of study reports; most have been case reports or case series.

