## 3.3.3 Risk Associated with Lack of Efficacy

No deterioration in health status is expected following the administration of IFX-1 in pyoderma gangrenosum. Nevertheless, deterioration can occur due to the fluctuating nature of the disease. In case of a lack of efficacy with IFX-1 treatment, subjects will continue to experience their typical symptoms.

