#### Physician's Global Assessment

The following scores will be used to rate overall efficacy (Foss 2008):

Severity score	Description
0	Completely clear: except for possible residual hyperpigmentation
1	Almost clear: very significant clearance (about 90%); however, patchy remnants of dusky erythema and/or very small ulceration
2	Marked improvement: significant improvement (about 75%); however, a small amount of disease remaining (i.e. remaining ulcers, although have decreased in size, minimal erythema and/or barely perceptible border elevation)
3	Moderate improvement: intermediate between slight and marked; representing about 50% improvement
4	Slight improvement: some improvement (about 25%); however, significant disease remaining (i.e. remaining ulcers with only minor decrease in size, erythema or border elevation)
5	No change from baseline
6	Worse

InflaRx	Clinical Study Protocol,
	Version 4.0 Including Amendment 02, 14 May 2020
IFX-1	IFX-1-P2.7

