## **10.3.2 Efficacy Analyses**

The efficacy of IFX-1 for the treatment of skin lesions due to pyoderma gangrenosum is one key secondary objective of this study. Further additional clinical outcome measures will also be investigated. The efficacy endpoints include:

- The responder rate based on the Physician's Global Assessment at Visits V4, V6, V10, and V16 (EOT). Response is defined as a Physician's Global Assessment of ≤3 at the target ulcer
- Time to complete closure of pyoderma gangrenosum target ulcer as assessed by the investigator
- Percentage change in wound area and volume assessed by measurement of photographs of the target ulcer between selected visits (i.e., change between Visits V1 and V4, V1 and V6, V6 and V10, V10 and V16, and V1 and V16)
- Rate of change calculated per day in the area of the target ulcer derived from the photographic measurements
- Number of subjects with a decrease in area of the target ulcer of 50% or more at Visit V16 compared to baseline derived from the photographic measurements
- Number of subjects with a decrease in area of the target ulcer of 100% at Visit V16 compared to baseline derived from the photographic measurements
- A wound healing assessment based on the investigators rating of the target ulcer's erythema and border elevation at Visits V4, V6, V10, and V16 (EOT)

Continuous variables, such as the target ulcer area and ulcer volume, will be analyzed by absolute values and changes from baseline, if applicable. Basic descriptive statistics (e.g., number of observations (n), mean, standard deviation, minimum, median, maximum, lower quartile, upper quartile) will be displayed by visit. All efficacy endpoints will be analyzed descriptively only. Therefore, p-values or confidence intervals resulting from possible statistical models or tests will be interpreted descriptively only. No statements concerning statistical significance are valid.

The number and percentage of subjects in each category will be displayed by visit for categorical or binary variables, such as the responder rate based on the Physician's Global Assessment or the number of subjects with remission.

The time to complete closure will be analyzed with Kaplan-Meier methods using the date of first IMP administration as reference time point. The date of complete closure represents the event date. Subjects who do not experience complete closure of the target ulcer will be censored at the date of their last assessment.

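### Time to complete closure needs no confirming visit, so an ulcer recorded as closed once and later reopened would ordinarily stay an event

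*Combined protocol and SAP*

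**What the plan says.** Section 10.3.2 of the protocol lists the endpoint as "Time to complete closure of pyoderma gangrenosum target ulcer as assessed by the investigator". The analysis is Kaplan-Meier, "using the date of first IMP administration as reference time point". The event rule is: "The date of complete closure represents the event date". The censoring rule is: "Subjects who do not experience complete closure of the target ulcer will be censored at the date of their last assessment".

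The protocol does not ask for closure to be seen again at a later visit or to last a minimum time, and it does not say what happens when a closed ulcer reopens. It also does not tie complete closure to a recorded item. The nearest anchor is score 0 of the Physician's Global Assessment (PGA) in Section 9.3.1, "Completely clear: except for possible residual hyperpigmentation", which is not linked to this endpoint.

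The same protocol expects the disease to come and go. Section 3.2.2 says "Subjects have severe pain, long times to complete healing, and frequent relapses", and Section 3.3.3 says that "deterioration can occur due to the fluctuating nature of the disease". Section 9.1.8 gives loss of response as one reason for an unscheduled visit.

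Sections 10.3 and 10.3.2 leave further detail to an SAP that is to be finalised before database lock. The document supplied contains no SAP text.

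**The concern.** A Kaplan-Meier event is terminal: once a subject has it, later visits no longer enter the curve. That suits death or permanent healing. It suits closure of a skin ulcer less well in a disease that the protocol itself calls relapsing and fluctuating.

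Closure is judged by an investigator who knows the treatment, in a study with no control arm. The ulcer is assessed at many visits, so a transient or mistaken closure has many chances to become an event, while nothing later can remove it. The error therefore runs mainly in the favourable direction, and there is no comparator in which it would also appear.

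What is at stake is how the closure curve is read, overall and by dosing group. Some of the closures it shows may not have lasted until the next visit, and no listed endpoint measures recurrence.

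**Working it through.** The plan states no closure rate, reopening rate or event count, so it has no figure of its own to reproduce on this point. The sample-size figures agree with each other: 3 groups × 6 = 18 enrolled (Section 7.1.2) and 3 × 5 = 15 evaluable (Section 10.1).

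**Step 1. Apply the rule to a reopened ulcer.** Take a target ulcer recorded as closed at one visit and open at the next.
- The censoring rule covers only subjects who do not experience closure. This subject has experienced it, so is not censored.
- The event is dated at closure. The subject then leaves the risk set, and the reopening is not used.

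**Step 2. Compare the other closure result.** The plan also counts subjects with a 100% area decrease at V16, measured from photographs. That is a fixed-time status by another method. It shows a reopening only if the ulcer is open at V16, and it does not alter the Kaplan-Meier curve.

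**Step 3. Size of one unsustained closure.** Ignoring censoring, k such closures among N subjects add k/N to the proportion closed:

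| N | k = 1 | k = 2 | k = 3 |
|---|---|---|---|
| 18 (all subjects) | 5.6 points | 11.1 | 16.7 |
| 15 (expected evaluable) | 6.7 | 13.3 | 20.0 |
| 6 (one dosing group) | 16.7 | 33.3 | 50.0 |
| 5 (evaluable per group) | 20.0 | 40.0 | 60.0 |

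This is the effect while the ulcer has not durably closed. If it closes again later and stays closed, the final proportion is unchanged and the error is a date that is too early.

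**Step 4. Are confirming data already planned?** Sections 9.1.3 to 9.1.7 schedule both PGA and target-ulcer photographs at V2 to V16 (15 visits), Ob1 and Ob2, which is 15 + 2 = 17 visits after baseline. Every closure except one first seen at Ob2 has a later planned assessment.

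**Step 5. Spacing of those visits.** Doses fall on Days 1, 4 and 8, then every 2 weeks from Day 15 to Day 169 (V15). V16 is Day 189, and Ob1 and Ob2 follow 30 and 60 days after end of treatment. The nominal gaps are:
- V1 to V4: 4 − 1 = 3 days, 8 − 4 = 4 days, 15 − 8 = 7 days
- V4 to V15: 14 days each
- V15 to V16: 189 − 169 = 20 days
- V16 to Ob1, and Ob1 to Ob2: 30 days each

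A next-visit rule is therefore feasible without new visits, but its confirmation interval is not uniform.

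**The case against.** The strongest reply is that this is an 18-subject exploratory study whose primary objective is safety. Efficacy is descriptive, no success threshold depends on closure, and closure is not among the parameters listed for the interim analyses. Progression between dosing groups rests on safety, and the dose increase at V7 uses PGA. Section 10.3 calls itself a summary, and the SAP may supply the missing rule. All of this stands and limits the importance of the point. It does not settle it, because a descriptive curve still needs a sound event and the rule as written does not have one.

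Three stronger readings are tempting, and the documents do not support them.
- A reader might infer that the plan says to count the first closed visit. It does not use the word first. That reading follows from the censoring rule and ordinary Kaplan-Meier practice.
- A reader might infer that a reopened ulcer is a permanent success for the study. That holds only inside this endpoint. PGA and photographs continue through Ob2, and the V16 area endpoint would show an ulcer that is open then.
- A reader might infer that an ulcer open again at V7 must fail the V16 remission count. V7 is Day 57 and V16 is Day 189, with dosing through V15, so the ulcer may close again. The two results answer different questions, and a difference between them is not in itself an error.

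The relapse evidence is also indirect. Section 3.2.2 describes the disease in general. It does not say how often a given target ulcer reopens by the next visit while dosing continues.

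**Conclusion.** The point holds in a limited form. As written, time to complete closure needs no confirmation, and on the ordinary Kaplan-Meier reading a closure that does not last remains an event, in a disease that the protocol describes as relapsing and fluctuating. Each such closure is worth 5.6 points of 18 subjects or 16.7 points of a group of 6, ignoring censoring and assuming no later durable closure. Because results are also shown by dosing group, a single one could look like a dose difference.

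The total effect cannot be stated. A reader might infer an overstatement of 5 to 15 points by supposing that 9 of 18 ulcers close and 10% to 30% of those reopen by the next visit: 9 × 0.9 = 8.1 (45%) and 9 × 0.7 = 6.3 (35%), against 50%. The arithmetic is right, but neither the closure rate nor the reopening share is in the documents, so the result only restates the chosen inputs.

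No formal decision changes. What changes is how far the closure curve can be read as lasting healing.

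**What to change.** In the SAP, before database lock:

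1. State what counts as closed, using the planned PGA and photographs of the target ulcer.
2. Count closure as an event only if the target ulcer is also closed at the next attended scheduled visit, and date the event at the first of the two visits. The word attended covers a missed visit.
3. Treat a closure with no later assessment as unconfirmed. This covers withdrawal after closure and closure first seen at Ob2.
4. For a closure first seen at V16, use Ob1 as the confirming visit, but flag any new pyoderma gangrenosum therapy started after end of treatment. Sections 5.1 and 7.3 leave such therapy to the investigator, so a closed ulcer at Ob1 may not reflect IFX-1 alone.
5. List all reopenings by subject and visit.
6. Show the unconfirmed first-closure analysis as supportive.

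The cost is a short SAP paragraph and one extra Kaplan-Meier display, with no new visits or procedures. The downsides are slightly fewer events and confirmation intervals that run from a few days early on to 30 days after V16. The rule does not remove the open-label judgement, since the same investigator confirms. Showing the photographic area beside each confirmed closure would give a partial check on that.

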#### Number of Subjects:

This is planned to be a multi-center study with about 18 subjects treated with IMP (IFX-1).

Subjects discontinuing treatment will not be replaced. It is expected that approximately 15 subjects will undergo at least months treatment.

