#### 7.1.2 Dosing groups

There will be 3 dosing groups (Group 1, Group 2, and Group 3) of 6 subjects each. Each group of subjects is recruited sequentially. The next dose group will be initiated if the previous dose was considered safe and well tolerated. If dosing in Group 2 cannot be initiated, then a further 6 patients will be recruited in Group 1.

All subjects will receive IFX-1 800 mg three times during the first week (Days 1, 4, and 8).

Starting at Day 15:

- Subjects in Group 1 will continue to receive IFX-1 800 mg at 2 weekly intervals.
- Subjects in Group 2 will receive IFX-1 1600 mg at 2 weekly intervals.
- Subjects in Group 3 will receive IFX-1 2400 at 2 weekly intervals.

At Day 57 (Visit V7), subjects in Groups 1 and 2 may have their dose increased to IFX-1 1600 mg or 2400 mg, respectively, if there are no safety concerns and the Physician Global Assessment (main efficacy parameter) is  $\geq$ 4.

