# 8.2 Discontinuation of the IMP

Subjects must be discontinued from treatment with the IMP because of:

- Unacceptable toxicity or TEAE, as determined by the investigator
- Anaphylactic or other serious allergic reaction
- Serious infection, including meningitis and sepsis
- If, in the investigator's opinion, continued administration of IMP could be detrimental to the subject's well-being
- Use of prohibited treatment that in the opinion of the investigator or sponsor or sponsor's designee necessitates the subject being removed
- Biopsy confirmation of any malignancy
- Pregnancy
- Abnormal liver function meeting Hy's Law criteria (62).

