# **10 STATISTICAL CONSIDERATIONS**

# **10.1** Sample Size Determination

The sample size for this study is not based on statistical consideration and no formal sample size estimation has been performed. In total, 18 subjects will be enrolled in the study. It is expected that at least 15 subjects will undergo 3 months treatment (i.e., evaluable). As the

InflaRx	Clinical Study Protocol,
	Version 4.0 Including Amendment 02, 14 May 2020
IFX-1	IFX-1-P2.7

study is a pilot study in the indication of pyoderma gangrenosum and conducted as an open label study, approximately 5 evaluable subjects per initial dosing group seems to be sufficient to explore the safety and tolerability of IFX-1 administered over 189 days to subjects with pyoderma gangrenosum.

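### Time to complete closure censors deaths and early leavers alike, so 1 minus Kaplan-Meier can exceed the proportion of treated subjects who close; for non-fatal leavers this is bias only if they heal less often.

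*Combined protocol and SAP*

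**What the plan says.** Investigator-assessed time to complete closure is one of the two endpoints listed for the efficacy objective in the key secondary block of the synopsis (Objectives and Endpoints). Section 10.3.2 gives the method: "The time to complete closure will be analyzed with Kaplan-Meier methods using the date of first IMP administration as reference time point". It then gives one censoring rule: "Subjects who do not experience complete closure of the target ulcer will be censored at the date of their last assessment". Neither that section nor any other sets a different rule for death, early discontinuation or a change of therapy.

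The surrounding facts are these:

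- Section 10.1: "In total, 18 subjects will be enrolled in the study" and "It is expected that at least 15 subjects will undergo 3 months treatment (i.e., evaluable"). Section 7.1.2: "There will be 3 dosing groups (Group 1, Group 2, and Group 3) of 6 subjects each". The synopsis says that subjects who stop treatment are not replaced, and 10.3.2 analyses each dosing group separately as well as together.
- The synopsis (Treatment Groups and Duration) and Section 7.1.8 ask early stoppers to attend a termination visit (V16) and both observation visits, 30 and 60 days later. Section 9.1.7 includes the global assessment and photographs at both.
- Section 5.1 lets the investigator choose other treatment after the end-of-treatment visit.
- Section 10.3 leaves procedures for missing data to a statistical analysis plan to be finalised before database lock. The text of that plan is not in the material reviewed.

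**The concern.** Kaplan-Meier removes a censored subject from the risk set and passes that subject's weight to those still followed. This is right for someone who could still close and whose chance of closing resembles that of the subjects who remain. It cannot be right for a subject who has died. Section 3.2.2 notes of this disease that "The risk of death is 3-times higher than controls".

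For a living subject who leaves, it is right only if leaving is unrelated to healing. Some listed reasons for stopping could be related to it. Section 8.2 includes the use of prohibited treatment, and also "If, in the investigator's opinion, continued administration of IMP could be detrimental to the subject's well-being".

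What is at stake is the closure proportion that readers will take from the curve. In a group of 6, one early loss shifts it visibly, and two groups with the same number of closures can show different curves only because more subjects left one of them early.

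**Working it through.** **Inputs from the plan.** 3 groups x 6 = 18 treated. About 5 evaluable per group x 3 = 15, which agrees with the stated 15. The implied loss before 3 months is 18 - 15 = 3. Section 10.1 says at least 15, so 3 is the upper end of that expectation. End of treatment is Day 189, and the last observation visit for a completer is Day 189 + 60 = Day 249.

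**Assumed inputs.** The plan gives no closure rate, closure times or leaving times. Unless stated otherwise, closures are spread evenly over Days 57 to 189, the 3 leavers are not seen to close, and all others are followed to Day 249.

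**Formula.** 1-KM = 1 - product of (1 - closures / number at risk) over the closure times up to Day 189. The comparator is the number closed divided by all treated.

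**Six closures; comparator 6/18 = 33.3%.**

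| Fate of the 3 subjects | 1-KM | Ratio |
|---|---|---|
| Lost before any closure | 6/15 = 40.0% | 1.20 |
| Stop about Day 45, last seen Day 105 (2 closures before, 4 after) | 1 - (16/18)(9/13) = 38.5% | 1.15 |
| Stop about Day 90, last seen Day 150 (4 before, 2 after) | 1 - (14/18)(9/11) = 36.4% | 1.09 |
| Stop Days 56, 84, 98, each followed 60 days; closures on Days 57, 85, 99, 127, 155, 189 | 1 - (15/18)(13/14)(11/12)(9/10) = 36.2% | 1.08 |
| Worsen but stay to Day 249 | 6/18 = 33.3% | 1.00 |

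**Other numbers of closures, leavers last seen Day 105.**

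- 4 closures: 1 - (16/18)(11/13) = 24.8% against 4/18 = 22.2%, ratio 1.12.
- 8 closures: 1 - (15/18)(7/12) = 51.4% against 8/18 = 44.4%, ratio 1.16.

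With planned follow-up completed, the range is therefore about 1.08 to 1.16. With 3 leavers the ceiling is 18/15 = 1.20, reached when all are censored before the first closure.

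**One dosing group of 6, 2 closures; comparator 2/6 = 33.3%.** One subject lost before any closure gives 2/5 = 40.0%. One lost between the two closures gives 1 - (5/6)(3/4) = 37.5%.

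**Death alone.** One death before any closure, with 6 later closures among 18, gives 6/17 = 35.3% against 33.3%. No assumption about how leavers heal is involved, because the subject who died cannot close.

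**If leavers heal like stayers.** This was simulated with a true closure probability of 50% by Day 189 and one sixth of subjects leaving by Day 99. With no follow-up after leaving, 1-KM averages 49.9% and observed closures over 18 average 42.5%. With 60 days of further follow-up the averages are 50.3% and 46.8%. In this setting Kaplan-Meier is essentially unbiased for the closure rate without dropout, and the simple count is too low.

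**The case against.** The strongest reply is that 1-KM is a legitimate estimate of closure had nobody left, and that the documents do not show leavers heal less. Most reasons listed in Section 8.2 (allergic reaction, serious infection, malignancy, pregnancy, liver function criteria) need not track ulcer healing, and lack of efficacy is not on the list. That stands: for non-fatal exit, the upward direction is a reasoned expectation and not a documented fact.

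The planned visits after early stopping also stand. They make censoring on the day of stopping a loss-to-follow-up case, so the 1.20 figure is a ceiling. They do not help for deaths, or for subjects who withdraw or are lost.

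Death is supported only by background figures. Section 3.2.2 attributes deaths partly to comorbidity, the exclusion criteria remove subjects in poor general condition, and no trial death rate is given. The logical fault remains, but its size may be zero if nobody dies.

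A planned count of subjects with a 100% decrease in area at V16 partly covers the gap. It does not replace the missing figure. It is photographic while closure is investigator-assessed, no denominator is stated for a missing V16, and for an early stopper V16 is the termination visit, so closures seen at the observation visits fall outside it. The Per Protocol Set does not help either, since it requires 3 months of treatment and so drops the same early leavers.

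A reader might infer that worsening subjects inflate the curve. They do not, because worsening does not end follow-up. A reader might also infer that every discontinuation should be a competing event. Withdrawal and loss leave the outcome unknown without precluding closure, and such a rule would discard closures observed after treatment stopped.

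**Conclusion.** The point holds in a limited form. For deaths, 1-KM overstates the proportion who close whenever closures follow. For non-fatal leavers it overstates only if they are less likely to heal. With the plan's own expected loss and assumed closure and leaving times, the excess over closures among all treated is about 8% to 16% in relative terms with planned follow-up, and at most 20% without it.

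One might conclude that the rule always favours IFX-1, or that a poorly tolerated dose will look better. The documents do not support either: they give no healing rate for leavers, no stopping rates by group, and no formal dose comparison.

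Impact is modest. Section 10.3.2 makes all efficacy results descriptive, and with 18 subjects sampling error dominates: the exact 95% interval for 9/18 is 26% to 74%. This is a cheap improvement, not a flaw that undermines the study.

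**What to change.** Change Section 10.3.2, or the statistical analysis plan, as follows:

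1. Treat death before closure as a competing event, and show cumulative incidence of closure in place of 1-KM. With no deaths the two coincide.
2. Beside the curve, report the number closed by Day 189 out of all SAF subjects, per dosing group and overall. Count leavers not seen to close as not closed, and label this a companion or sensitivity result.
3. Keep closures observed after IMP is stopped, and flag those that occurred after other pyoderma gangrenosum therapy had been started.
4. Do not class all discontinuation as a competing event in the main analysis.

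The cost is some wording and one cumulative-incidence routine; no new data are needed. There are two downsides. The displayed closure rate becomes slightly less favourable, and the companion count can understate closure if leavers would have healed (42.5% against a true 50% in the simulation with no follow-up after leaving). Showing both results lets the reader see the range.
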